7.1.2. Per Protocol Population (PP)

The PP population includes all subjects in the mITT who received at least 5 doses of study medication during the first 7 days of dosing including the day prior to Day 8, have a Baseline and a Day 8 mLcVA measurement, and have no major protocol deviations considered to have significant impact on treatment outcome. The PP population will be used to analyze efficacy endpoints, with subjects included in their randomized treatment regardless of the treatment they actually received.

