	
Before further screening criteria, the following assessments shall be performed to establish baseline values:
 
• Mesopic high-contrast visual acuity (mHCVA), photopic low-contrast visual acuity (pLCVA), and mesopic high-contrast distance-corrected near visual acuity (DCNVA)• Using an [REDACTED] [REDACTED] and corneal topography measurements under [REDACTED]• Conjunctival hyperemia, assessed visually with a grading scale (0-3) using images from the Cornea and Contact Lens Research Unit (CCLRU; Investigators are cautioned to appropriately note all observations of conjunctival hyperemia on the biomicroscopy electronic Case Report Form at screening)• Slit lamp biomicroscopy 
The subject must also meet dry eye Exclusion Criterion #13 to be included in the study at the determination of the investigator. Specifically, subjects with undiagnosed dry eye may undergo a dry eye test.
 
Final screening must include IOP measurement (using a Tono-Pen) and ophthalmoscopy.
 
With the subject passing all eligibility criteria, the Screening Visit becomes the Baseline Visit. The subject will then be assigned a randomization number and randomized into the study.
 
See Table 2 for details on measurements expected at each visit. The first dose of study medication must be taken by the subject at 8PM to 10PM on the Baseline Visit (Day 1). All treatments will be administered OU.

Treatment Visits	Treatment visits will occur 2 times: Day 8 (± 1 day)/Visit 2 and Day 15 (± 1 day)/Visit 3. mLCVA evaluations shall be performed on each of these days. [REDACTED] [REDACTED] Other assessments as defined in Table 2 shall be performed at these visits.
Follow-up Visit	A follow-up visit (Visit 4) phone call will occur 1 to 3 days after Visit 3. Concomitant medications and adverse events (AEs) will be collected.

study eye, the best of either eye, and binocular) shall be collected and analyzed for the sites that have an OPD Scanner and will include but are not limited to:

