4.5 Expected Duration of Subject Participation

The total length of subject participation is approximately 3 weeks, with 3 clinic visits and one telephone call follow-up summarized below:

- Visit 1 (Screening/Baseline)/Day 1
- Visit 2 (Treatment)/Day 8 (± 1 day)
- Visit 3 (Treatment)/Day 15 (± 1 day)
- Follow-up telephone call 1 to 3 days after Visit 3

The execution of the entire study (first subject screened through last randomized subject completed) is expected to be approximately 9 to 12 months.

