The subjects will be asked if they had any problems with their eyes since the last visit, and if there have been any changes in their medical condition or concomitant medications since their last visit. *Any adverse changes in the condition of the subject are recorded as an AE.*

In addition, at Visit 2 subjects shall have the following assessments, as defined in [Table 2](#):

- Females of childbearing potential must take a urine pregnancy test.
- Subject must have HR and BP assessments.
- Subject shall be assessed using the subject questionnaire.
- Pupil diameter
- Subject shall be assessed for mLcVA, mHCVA, pLCVA and DCNVA (mesopic, high-contrast conditions) as mentioned in [Section 4.1](#).
- OPD Scan measurements (for those sites with OPD Scan III), wavefront aberrometry (total and higher-order RMS) and corneal topography measurements under mesopic conditions, and other data captured
- Eye redness (conjunctival hyperemia) will be assessed visually with a grading scale (0-3) using images from the CCLRU.
- Subject will have an IOP assessment.

7.2.3 *Visit 3 (Treatment)/Day 15 (± 1 day)*

During the second week of treatment, subjects will continue to administer 1 drop of study medication OU every night using a new bottle for each dose, then emptying the remaining contents of that bottle, return the opened bottle to its foil pouch and place it in the medication box for return to the study site at their next visit.

If the subject wears contact lenses, they must be removed for a minimum of 8 hours prior to ophthalmic assessments. At Visit 3, the subject will bring their used dropper bottles with any unused medications and diary with them for purposes of drug accountability. The last day of study treatment is the day before Visit 3; no further study medication will be dispensed at Visit 3.

The subjects will be asked if they had any problems with their eyes from the last visit, and if there have been any changes in their medical condition or concomitant medications since their last visit. ***Any adverse changes in the condition of the subject are recorded as an AE.***

In addition, at Visit 3 subjects will have the following assessments, as defined in [Table 2](#):

- Females of childbearing potential must take a urine pregnancy test.
- Subject must have HR and BP assessments.
- Subject shall be assessed using the subject questionnaire.
- Pupil diameter

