- Subject shall be assessed for mLcVA, mHCVA, pLCVA, and DCNVA (mesopic, high-contrast conditions) as mentioned in [Section 4.1](#).
- OPD Scan measurements (for those sites with OPD Scan III), wavefront aberrometry (total and higher-order RMS) and corneal topography measurements under mesopic conditions, and other data captured
- Eye redness (conjunctival hyperemia) shall be assessed visually with a grading scale (0-3) using images from the CCLRU.
- Subject shall be assessed using biomicroscopy.
- Subject must have an IOP assessment.
- Subject shall be assessed using ophthalmoscopy.

7.2.4 *Follow-Up Phone Call Visit 4*

Up to 3 days after Visit 3, subjects will be called and asked if they had any problems with their eyes from the last visit, including whether their eyes are red, and if there have been any changes in their medical condition or concomitant medications since their last visit.

Any changes in the condition of the subject are recorded as an AE.

If an AE/adverse reaction is unresolved at the time of the last visit or if a subject reports a worsening of symptoms, every effort should be made to follow up until the AE/adverse reaction is resolved or stabilized, the subject is lost to follow-up, or there is other resolution to the event.

7.2.5 *Unscheduled Visits*

An Unscheduled Visit may be any visit to the Investigator other than the specific visits requested in the protocol as possibly required for the subject's ophthalmic condition. The Investigator will perform all procedures necessary to evaluate the study participant at these visits and record any AEs in the eCRF.

As noted in [Section 4.9.4](#), every possible effort should be made by Investigators to assure that subjects who discontinue early from the study have a telephone follow-up that includes assessments of AEs, concomitant medications, and subject-evaluated conjunctival hyperemia.

7.2.6 *Visit Variation*

Visit 2 on Day 8 and Visit 3 on Day 15 may each be 1 day late. If the visit is late, the subject should be advised to take an additional dose from 1 of the 2 spare dropper bottles provided in the study medication box the night before the visit. The subject should then empty the remaining contents and return the opened bottle to its foil pouch and place it in the medication box for return to the study site at their next visit. The follow-up telephone call may occur up to 3 days after Visit 3.

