Efficacy will be assessed using the mITT and PP population with subjects included in the treatment arm in which they were randomized. For the analysis of the primary efficacy endpoint, appropriate imputation techniques will be performed for missing observations if applicable; details will be provided in the study Statistical Analysis Plan. If the analysis using the PP population shows a positive effect for Nyxol at the 0.05 level of significance, the primary endpoint will be considered met. Confirmatory analyses may be performed using the ARP, with imputation performed for missing data. For the analysis of the secondary efficacy endpoints, only observed case data will be used. If warranted, confirmatory analyses using the ARP with imputation for missing data will also be performed for the secondary efficacy endpoints.

For all efficacy endpoints, Baseline values are defined as the screening assessment values on Visit 1 (Day 1).

Secondary efficacy endpoints are indicated in [Section 4.1](#).

Each of the continuous secondary efficacy endpoints will be analyzed using analysis of covariance (ANCOVA) with change from baseline as the dependent variable, treatment, [REDACTED], and the respective baseline value included as the covariate. Each ANCOVA will be performed using the mITT and PP population, with subjects included in their randomized treatment regardless of the treatment they actually received. The output from each ANCOVA will include the least squares mean (LSM) and standard error for both treatment groups, along with the placebo-corrected LSM, its 95% CI and associated p-value.

For each of the secondary endpoints related to percent of subjects achieving certain criteria, the analysis will be performed using a logistic regression model with treatment, light/dark irides, and the respective baseline as a covariate. For each analysis, the percentage of subjects in each treatment group meeting the criteria, the OR with 95% CI and p-value will be provided. For these endpoints, the mITT and PP population will be used with subjects included in their randomized treatment regardless of the treatment they actually received.

In addition, each secondary efficacy endpoint will be analyzed [REDACTED] using the same model and sensitivity analysis indicated above, as appropriate. Other subgroups, such as age, sex, and race, may be analyzed as well.

9.3.6 *Analysis of Safety*

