9.1.1. Primary Efficacy Analysis

[REDACTED]

[REDACTED]

[REDACTED]

By including [REDACTED] primary efficacy analysis model, the model efficiency as well as a change in the treatment effect will be increased. Including this factor in the model will also make the results more generalizable to other studies in which the sample characteristics may differ from the current study [2]. Additionally, a sensitivity analysis will be applied to the primary efficacy endpoint for the mITT and PP populations,

which uses a logistic regression model with only treatment as a [REDACTED] [REDACTED].

For the analysis of the PP Population, subjects who did not dose the night before, or the morning of, their Day 15 visit will be excluded from the Day 15 visit summary.

In addition, the primary efficacy endpoint [REDACTED] using the same model indicated above [REDACTED]. For these subgroup analyses, observed case data only will be used; that is, missing values will not be imputed.

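### The per-protocol dosing rule is tied to nominal Day 8 although Visit 2 may fall on Day 7, 8 or 9, so off-day visits can be misclassified in both directions

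*SAP*

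**What the plan says.** **PP rule.** SAP 7.1.2 requires that the subject "received at least 5 doses of study medication during the first 7 days of dosing including the day prior to Day 8", has a Baseline and a Day 8 acuity measurement, and has no major deviation judged to affect outcome. Protocol 9.2 has the same dosing rule.

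**Visit timing.** The protocol synopsis states: "Treatment visits will occur 2 times: Day 8 (± 1 day)/Visit 2 and Day 15 (± 1 day)/Visit 3". Protocol 4.5 and the headings of 7.2.2 and 7.2.3 give the same window. Protocol 7.2.6 mentions lateness only: "Visit 2 on Day 8 and Visit 3 on Day 15 may each be 1 day late". It adds: "If the visit is late, the subject should be advised to take an additional dose from 1 of the 2 spare dropper bottles", to be taken the night before the visit.

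**Dosing.** Protocol 4.4.3 and 6.1 schedule one dose each evening between 8PM and 10PM, starting on the evening of Day 1. On the end of treatment, Protocol 7.2.3 says: "The last day of study treatment is the day before Visit 3".

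**Day 15.** SAP 9.1.1 has a PP rule for that visit alone: "subjects who did not dose the night before, or the morning of, their Day 15 visit will be excluded" from the Day 15 summary.

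**Role of PP.** SAP section 9 lets the mITT result decide whether the primary endpoint is met, and SAP 7.1.1 and Protocol 9.2 assign the primary analysis to the mITT. Protocol 9.3.5 instead begins its success criterion with "If the analysis using the PP population shows a positive effect for Nyxol at the 0.05 level of significance".

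**The concern.** A PP analysis should describe subjects who were dosed as planned up to the assessment. Here the dose clause is fixed to a study day, while the assessment may be a day earlier or later.

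- **Day 9 visit:** the evening before is Day 8, the eighth dosing evening, which the rule neither counts nor requires.
- **Day 7 visit:** the evening before is Day 6, which is not specifically required. The evening that is required, Day 7, comes after the measurement, so membership can depend on something that happened after the outcome was known.

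At stake is whether the PP estimate at the primary visit means what its label says. If Nyxol subjects who were not recently dosed respond less, keeping them would pull the PP difference towards zero.

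**Working it through.** The plan states no figure for this point, so the check is a count of dosing patterns and of hours.

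**1. Patterns under the literal rule** (night 7 dosed, at least 5 of nights 1-7; doses start on the evening of Day 1).

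- Night 7 is fixed, so at least 4 of nights 1-6 are needed: C(6,4) + C(6,5) + C(6,6) = 15 + 6 + 1 = 22 qualifying patterns.
- Day 8 visit: the night before is night 7, always dosed. Undosed: 0 of 22.
- Day 9 visit: night 8 is free, giving 22 × 2 = 44 patterns. Undosed the night before: 22 of 44.
- Day 7 visit: with night 6 missed, at least 4 of nights 1-5 are needed: 5 + 1 = 6. Undosed the night before: 6 of 22. A qualifying subject may have had only 4 doses before the measurement.

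**2. Illustrative shares.** The documents give no adherence figure. Assume each night is taken independently with probability p.

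| | p = 0.95 | p = 0.90 | p = 0.80 |
|---|---|---|---|
| Day 9 visit: PP subjects undosed the night before | 5% | 10% | 20% |
| Day 7 visit: PP subjects undosed the night before | 4.9% | 9.3% | 16.4% |
| Day 9 visit: excluded although dosed the night before with at least 5 earlier doses in all | 4.9% | 10.0% | 19.7% |
| Day 7 visit: same | 4.6% | 8.3% | 11.8% |

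The first two rows are shares of PP subjects with that visit day; the last two are shares of all subjects with that visit day. In the last two rows, the count of at least 5 is of doses taken before the visit, the night-before dose included.

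**3. Possible number, Day 9 visits.** The plan expects 136 evaluable subjects (160 × 0.85 = 136). Assume 10-30% are seen on Day 9. Undosed the night before = 136 × share × (1 − p):

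- low: 136 × 0.10 × 0.05 = 0.7
- high: 136 × 0.30 × 0.20 = 8.2

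Not all of these meet the PP dose rule. The proportion that do is p × P(at least 4 of 6 nights): 0.95 × 0.998 = 0.948 and 0.80 × 0.901 = 0.721. That leaves 0.7 × 0.948 ≈ 0.6 to 8.2 × 0.721 ≈ 5.9, both arms together. Day 7 visits would add to this.

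**4. Hours since last dose when the night before was missed.** Last dose at 8-10PM two evenings earlier:

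- 8AM visit: 34-36 h
- 10AM visit: 36-38 h
- 5PM visit: 43-45 h

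A subject dosed the night before is at 10-12, 12-14 and 19-21 h. The visit sections set no clock time, so these hours are illustrations. For a Day 7 visit the gap can be longer, since night 5 may be missed as well.

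**5. Does another reading of Day 8 solve it?**

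| Reading | Result |
|---|---|
| Calendar day in the dose clause, visit label in the measurement clause | Steps 1-4 apply |
| Visit label in both | Day 9 visit: the required evening is the eighth dosing day, but the clause places it within the first seven. Day 7 visit: the night before is required, but the count of 5 may still include a dose taken after the measurement |
| Calendar day in both | Every subject seen on Day 7 or 9 has no Day 8 measurement and leaves PP |

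No reading fits the visit window. If the words after the count only describe the window and do not require the last dose, even a Day 8 visit admits 7 of 29 patterns undosed the night before.

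**6. Visit-anchored rule.** With at least 5 doses before the actual visit, including the evening before it, the undosed share is 0 for visits on Day 7, 8 and 9.

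**The case against.** The best defence is that Day 8 is the plan's name for Visit 2: the endpoint and the measurement clause both use it that way. On that reading the last required dose is the one the night before the visit, and most of the problem goes. That stands as the probable intent, but the wording then contradicts itself for a Day 9 visit, and a programmer must choose.

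Other safeguards exist. Protocol 7.2.6 advises a dose the night before a late visit, so the Day 9 case needs that advice to be missed. SAP 9.1.2 summarises acuity improvement and pupil change by time since last dose, which would expose the mixture. Under SAP 8.2 a blinded review may remove subjects from PP, although that is discretionary and Protocol 12.3 does not list a missed dose among its examples. SAP 8.6 on compliance is redacted and may add rules.

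Three stronger readings are tempting and are not supported:

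- **That the Day 15 morning-dose clause helps cause the Day 8 problem.** It governs only the Day 15 PP summary. It may classify what subjects actually did without scheduling a dose, but it names a time that the dosing text does not contain, so it is a separate point to reconcile.
- **That trial success turns on this rule.** SAP section 9, SAP 7.1.1 and Protocol 9.2 rely on the mITT. Protocol 9.3.5 disagrees, which is a conflict in its own right.
- **That the drug effect is gone by 34-38 h.** The protocol reports pupil effect at 24 h in one earlier trial and sustained to 36 h in another. Neither is an acuity result or a stated limit.

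**Conclusion.** The point holds for the Day 8 rule as written. It is correct for a visit on Day 8 and misclassifies in both directions when Visit 2 is a day early or late: it can retain subjects undosed the night before, and it can exclude adequately dosed ones, for a Day 7 visit because of an event after the outcome.

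The number affected is unknown and probably small. The estimate of about 0.6 to 5.9 PP subjects with Day 9 visits rests on assumed independent adherence of 0.80-0.95 and an assumed 10-30% of visits on Day 9. No effect on power can be computed, because the response rates are redacted. Under the SAP the consequence is confined to a supportive analysis; retaining less responsive Nyxol subjects would weaken the PP difference and would not create a false positive.

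Two further inconsistencies stand beside this and do not cause it: the Day 15 morning-dose wording against evening dosing that ends the day before Visit 3, and late-only visits in Protocol 7.2.6 against ±1 day elsewhere. A reader might infer that 7.2.6 forbids early visits. It does not say so; it is silent on them.

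**What to change.** Before unmasking, and before the PP exclusion file is finalised, restate the dosing part of SAP 7.1.2 by the actual Visit 2 date: at least 5 doses before that visit, including the evening before it, derived from diary date/times. State that the Day 8 measurement means the Visit 2 measurement within the window. The team should confirm that it wants the count of 5 for all visit days, since it then means 5 of 6 evenings for a Day 7 visit and 5 of 8 for a Day 9 visit. Carry the wording into Protocol 9.2 or list it among the changes in SAP 3.3.

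Separately, reconcile the morning-dose clause in SAP 9.1.1 with the dosing sections, and Protocol 7.2.6 with the ±1 day window. This concerns analysis definitions only; no dosing rule is proposed.

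The cost is a few sentences and one derivation. SAP 9.1.2 already uses the diary date and time of the most recent dose at both visits. PP may lose or gain a few subjects. The sample size and the mITT analysis do not change.

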7.1.3. All Randomized Population (ARP)

The ARP will include all randomized subjects. This population is also known as the Intention-To-Treat (ITT) population. The ARP will be used in confirmatory efficacy analyses, with subjects included in their randomized treatment regardless of the treatment they actually received.

7.1.4. Safety Population (SP)

The SP will include all randomized subjects who have received at least one dose of study medication. The SP will be used to summarize safety variables, using the actual treatment a subject received.

7.2. Covariates and Subgroups

7.2.1. Planned Covariates

Planned covariates include baseline values for the given assessment.

7.2.2. Planned Subgroups

Subgroup analyses by [REDACTED]

select efficacy endpoints. Other possible subgroups include sex and race.

7.3. Management of Analysis Data

7.3.1. Data Handling

Data from unscheduled visits will not be included in the analysis of efficacy or safety but will be listed.

7.3.2. Missing Data

The primary efficacy endpoint is the percent of subjects with ≥ 15 ETDRS letters (≥ 3 lines) of improvement in the study eye compared to baseline in monocular mLcVA at Day 8. For the analysis of the primary efficacy endpoint, imputation will be performed for missing efficacy data as specified in [Section 7.3.2.3](#) for the analysis using the mITT. Confirmatory analyses will be performed using the ARP, also using imputation for missing data.

Otherwise, there will be no substitutions made to accommodate missing data points for efficacy data. All data recorded on the CRF will be included in data listings that will accompany the CSR.

Safety data will be imputed in limited situations. If the severity of an AE is missing, then the severity will remain missing. If relationship of the AE to study drug is missing, the relationship will remain missing. Missing or partial dates for AEs or concomitant medications will be imputed as described in [Section 7.3.2.1](#). Otherwise, all summaries of safety endpoints will be completed using observed cases in the SP; no imputation will be completed.

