2. LIST OF ABBREVIATIONS AND DEFINITION OF TERMS

Only abbreviations and terms relevant to the SAP are repeated herein. The reader is referred to the protocol for the complete and comprehensive list of abbreviations and definitions of terms for the study.

| Abbreviation/Term | Definition |
|-------------------|---|
| ADaM | Analysis Data Model |
| AE | adverse event |
| ANCOVA | analysis of covariance |
| ARP | All Randomized Population |
| ATC | Anatomical Therapeutic Chemical |
| BAT | Brightness Acuity Tester |
| BCDVA | best-corrected distance visual acuity |
| BP | blood pressure |
| CCLRU | Cornea and Contact Lens Research Unit |
| CDISC | Clinical Data Interchange Standards Consortium |
| CI | confidence interval |
| CRF | Case Report Form |
| CSR | Clinical Study Report |
| DCNVA | distance-corrected near visual acuity |
| DD | drug dictionary |
| DLD | dim light vision disturbances |
| EDC | electronic data capture |
| ETDRS | Early Treatment Diabetic Retinopathy Study |
| HR | heart rate |
| IOP | Intraocular pressure |
| ITT | Intention-To-Treat |
| LOCF | last observation carried forward |
| logMAR | logarithm of the minimum angle of resolution |
| LSM | least squares mean |
| MAR | missing at random |
| MCMC | Markov Chain Monte Carlo |
| MedDRA | Medical Dictionary for Regulatory Activities |
| mHCVA | mesopic high-contrast visual acuity |
| mITT | Modified Intention-To-Treat |
| Nyxol | Phentolamine Mesylate Ophthalmic Solution 1% (Nyxol®) |

| Abbreviation/Term | Definition |
|--------------------------|-------------------------------------|
| OD | right eye |
| OPD | optical path difference |
| OR | odds ratio |
| OS | left eye |
| OU | both eyes |
| PD | pupil diameter |
| pLCVA | photopic low-contrast visual acuity |
| PP | Per Protocol |
| PT | preferred term |
| QD | once daily |
| RMS | root-mean square |
| SAE | serious adverse event |
| SAP | Statistical Analysis Plan |
| SDTM | Study Data Tabulation Model |
| SE | standard error |
| SOC | system organ class |
| SP | Safety Population |
| TEAE | treatment-emergent adverse event |
| TFL | tables, figures, and listings |
| VA | visual acuity |
| WHO | World Health Organization |

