7.1.1. Modified Intention-to-Treat (mITT)

The mITT will include all randomized subjects who received at least 1 dose of study medication and have a Baseline and any Day 8 efficacy measurement. The mITT will be used for the primary endpoint analysis and to analyze efficacy endpoints, with subjects included in their randomized treatment regardless of the treatment they actually received.

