7.3.2.2. Missing Baseline Data

Every effort will be made to ensure that accurate baseline information on the subjects is collected. In the event that a subject is missing baseline information, the subject will be included in the SP for assessment of safety and excluded from the primary analyses. Each case of missing baseline data will be evaluated for potential inclusion in the exploratory endpoints. All baseline data will be observed cases, without imputation.

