7.3.2.3. Imputation Methods

[REDACTED]

[REDACTED]

[REDACTED]

[REDACTED]

The imputations will be done separately for each treatment group and will include the following variables in the imputation model: mLcVA at baseline and Day 8.

The number of imputations [REDACTED]. The change from baseline will be calculated from these imputed datasets. The observed outcome ([REDACTED]) for each imputed dataset will be [REDACTED]. See [Section 9.1](#) for details on these models. The estimates

and standard errors (SEs) of the odds ratios based on the

Example SAS code is provided below:

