9. EFFICACY ANALYSES

Unless otherwise noted, efficacy will be assessed using the mITT and PP populations, with subjects included in their randomized treatment regardless of the treatment they actually received. For the analysis of the primary efficacy endpoint, imputation will be performed for missing data as described in [Section 7.3.2.3](#). If the analysis using the mITT Population shows a positive effect for Nyxol at the 0.05 level of significance, the primary endpoint will be considered met.

Confirmatory analysis of the primary efficacy endpoint will be performed using the ARP, also using imputation for missing data. For the analysis of the secondary efficacy endpoints, only observed case data will be used.

To formally test the significance of endpoints of interest beyond primary efficacy, endpoints will be tested in a predefined sequence using observed data only, each at the significance level 0.05, until the first nonsignificant test. The primary efficacy endpoint will be first in this sequence. The endpoints in the sequence are for the mITT population and study eye, and either Day 8 or Day 15. The sequence is specified in [Section 12.3](#).

All efficacy assessment data, regardless of whether they are included in the analysis, will be presented in by-subject listings.

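### On the readable text, the all-randomized confirmatory analysis appears to impute missing Day 8 outcomes from the subject's own arm, so it adds little check on the missing-data assumption

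*SAP*

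**What the plan says.** - **ARP analysis.** SAP 7.3.2: "Confirmatory analyses will be performed using the ARP, also using imputation for missing data". SAP 9: "Confirmatory analysis of the primary efficacy endpoint will be performed using the ARP, also using imputation for missing data". Neither sentence names a method for this population.
- **Who is in the ARP.** SAP 7.1.3: "The ARP will include all randomized subjects".
- **Who is in the mITT.** SAP 7.1.1: "all randomized subjects who received at least 1 dose of study medication and have a Baseline and any Day 8 efficacy measurement". Few mITT subjects can therefore lack the primary outcome: only those with some other Day 8 efficacy measurement but no Day 8 mLCVA.
- **Imputation rule.** SAP 7.3.2.3: "The imputations will be done separately for each treatment group", with these "variables in the imputation model: mLcVA at baseline and Day 8". Dosing status and reason for withdrawal are not listed. Several lines of this section are redacted.
- **Missing baseline.** SAP 7.3.2.2 does not impute baselines, and subjects without one are "excluded from the primary analyses".
- **Early termination.** SAP 7.3.3 assigns early-termination data to the nearest of Day 8 and Day 15, so some withdrawn subjects will have a Day 8 value.
- **Sensitivity analysis.** The one that can be read in SAP 9.1.1 drops terms from the logistic model. It leaves the missing-data assumption unchanged.

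**The concern.** An all-randomized analysis is useful because it brings back subjects whom the main analysis leaves out. Here these are mostly people who never dosed or who left without a Day 8 measurement. Under Protocol 7.2.1, baseline is measured before randomization and the first dose is taken at home that evening. A never-dosed subject therefore has a baseline and can be imputed.

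If the by-arm rule is used, that subject's Day 8 value is drawn from a model fitted to Nyxol subjects who were measured. The analysis then assumes that the missing subjects respond like the observed ones in their arm, which the observed-case result assumes too. Agreement between the two would say little about whether that assumption is safe. The question matters because Protocol 2.2 gives conjunctival hyperemia and ocular irritation as the most common adverse events on Nyxol, so loss related to treatment is plausible.

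**Working it through.** **1. The plan's own figure.** SAP 6 needs 136 evaluable subjects and assumes 15% drop-out: 136 / (1 - 0.15) = 160. This reproduces, and gives 80 randomized and 68 evaluable per arm, so at most about 12 missing per arm if losses are balanced. The Phase 3 response rates are redacted, so all rates below are assumptions.

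**2. Expected odds ratios.** Let p1 and p0 be the observed response rates on Nyxol and placebo, and m the missing fraction in each arm. OR(a, b) = [a/(1-a)] / [b/(1-b)].
- Own-arm imputation leaves the rates at p1 and p0, so the OR is unchanged.
- Placebo-based imputation gives (1-m)p1 + m·p0 on Nyxol and p0 on placebo.
- Missing = non-responder gives (1-m)p1 and (1-m)p0.

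Example with p1 = 19% (the Phase 2 Nyxol rate in Protocol 2.2), p0 = 5% (assumed) and m = 0.15:
- Own-arm: (0.19/0.81) / (0.05/0.95) = 4.46.
- Placebo-based: the Nyxol rate is (68 × 0.19 + 12 × 0.05) / 80 = 0.169, so the OR is 3.86.
- Non-responder: rates 0.1615 and 0.0425, so the OR is 4.34.

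| Assumed rates | Observed = own-arm | Placebo-based, 15% | Non-responder, 15% | Own-arm / placebo-based, 15% | Same ratio, 5% |
|---|---|---|---|---|---|
| 19% vs 5% | 4.46 | 3.86 | 4.34 | 1.15 | 1.05 |
| 25% vs 10% | 3.00 | 2.65 | 2.90 | 1.13 | 1.04 |
| 30% vs 10% | 3.86 | 3.33 | 3.68 | 1.16 | 1.05 |
| 40% vs 20% | 2.67 | 2.35 | 2.52 | 1.14 | 1.04 |

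If missing Nyxol subjects truly respond like placebo, the placebo-based column is the correct value and the ratio is the overstatement.

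**3. Simulation of the full procedure.** About 200 trials per scenario, 80 per arm, 20 imputations. Day 8 change was imputed by a Bayesian normal regression on baseline within arm. Response was a change of at least 15 letters, analysed by logistic regression and pooled by Rubin's rules. Assumptions: mean change 8.0 vs 3.1 letters (Phase 2, Protocol 2.2), SD 8, and missingness unrelated to baseline.

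With 12 of 80 missing per arm, and missing Nyxol subjects responding like placebo:
- Median OR: 3.50 observed-case, 3.53 own-arm, 3.02 placebo-based, 3.39 non-responder, and 2.96 had everyone been measured.
- Own-arm and observed-case log ORs correlated at 0.992. Within a trial the ratio of the two ORs ran from 0.87 to 1.11 (5th to 95th percentile), and the significance verdict agreed in 95.5% of trials.
- About 22% of missing Nyxol subjects were imputed as responders.
- The ratio of medians, 3.53 / 2.96 = 1.19, is above the range in step 2. With a Nyxol mean change of 10 letters it was 4.87 / 4.28 = 1.14. These medians carry simulation noise, so step 2 is the better guide to size.

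With 4 of 80 missing per arm: 3.33 observed-case, 3.35 own-arm and 3.25 full data (3.35 / 3.25 = 1.03), with verdict agreement of 99%.

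If missing Nyxol subjects in fact respond as treated (12 of 80 missing), own-arm imputation still follows the observed cases: 3.30 vs 3.28, ratio 0.83 to 1.11. It gives nearly the same answer whichever assumption is true.

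**4. Dependence on imbalance.** If 20 of the 24 planned losses fell on Nyxol, 12/60 vs 5/76 (20.0% vs 6.6%, Fisher p = 0.034) becomes 12/80 vs 5/80 (p = 0.12) under non-response. Placebo-based imputation gives (12 + 20 × 5/76) / 80 = 16.6% vs 6.6%. With balanced losses, 14/68 vs 5/68 (p = 0.046) becomes 14/80 vs 5/80 (p = 0.048). Only the unbalanced split changes the verdict.

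**The case against.** **The ARP method is not stated in the readable text.** SAP 7.3.2 ties Section 7.3.2.3 to the mITT and says only that the ARP also uses imputation. The redacted lines may hold an ARP rule. The SAP says it lists only relevant abbreviations, and the list includes LOCF, MCMC and MAR ("missing at random"), none of which is used in the readable body. Day 8 is the first post-baseline visit, so carrying the last value forward would normally mean zero change and hence non-response. This objection stands: the point depends on an inference, and a hidden rule would answer it. LOCF may equally be left over from a template.

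**Day 8 loss may be small.** The SAP's 15% runs to Day 15, early-termination data can fill Day 8, and Protocol 4.9.4 asks for every effort to obtain Day 8 mLCVA before a subject leaves. Protocol 9.1 does apply the 15% to subjects evaluable at Day 8, so 24 is a planning ceiling rather than a forecast. This also stands, and is why the 5% case is shown.

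**Stronger readings that the documents do not support.** A reader might infer that the ARP analysis must repeat the observed odds ratio exactly. It does so only in expectation, and could depart further if missing subjects have different baselines. A reader might also infer that it will be presented as independent proof of efficacy. No section says so: SAP 9 decides the primary endpoint on the mITT, and no success criterion depends on the ARP. Nor does the unbalanced example in step 4 show that significance would be lost, because it puts five-sixths of the losses on one arm.

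**Conclusion.** The concern holds, conditionally. If the by-arm rule in SAP 7.3.2.3 is the one used for the ARP, the only all-randomized efficacy analysis shares the missing-data assumption of the result it is meant to confirm, and no readable analysis varies that assumption. The overstatement of the odds ratio is about 13-16% at 15% missing Day 8 data and about 3-5% at 5%. These sizes rest on assumed response rates, equal missingness in the two arms, and a placebo-like response in missing Nyxol subjects. They would be larger if loss is concentrated on Nyxol. The mITT decision rule is not affected. What is missing is an informative robustness check.

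**What to change.** In SAP 7.3.2 and 9, state the ARP rule explicitly:
- Impute missing Day 8 mLCVA in both arms from the placebo-arm model.
- Add missing = non-responder as a supplementary table. It should not be the main check, because with balanced loss it barely moves the odds ratio (4.46 to 4.34, against 3.86 for placebo-based imputation).
- Describe the primary result as robust to missing data only if the placebo-based analysis agrees.
- Keep by-arm imputation for the mITT.

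If the unredacted SAP already contains a separate ARP rule, cite it in both sections and check it against this aim. The cost is SAP wording, one extra table and a somewhat less favourable ARP estimate. Trial conduct and the primary analysis do not change.
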